10.4 Exploratory Efficacy Variables

10.4.1 Assessment of Fat Pads and Injection Procedure

Descriptive

or summary statistics will be presented by treatment groups for each of these assessments as appropriate.

10.4.2 Quality of Life Outcomes

Each quality-of-life questionnaire discussed below will be completed by the participants at Screening (baseline), Day 30, Day 90, Day 180 or at early discontinuation visit if necessary.

Descriptive statistics for each of the aggregate measures and their corresponding change from baseline scores will be presented by treatment group at each visit.

The change from baseline in each of the aggregate scores will be analyzed using a mixed model for repeated measures (MMRM). The model will include treatment group, visit, age group, type of surgery, and treatment group by visit interaction as categorical fixed effects, and baseline score as a continuous fixed effect. Restricted maximum likelihood method will be used. The within-patient correlation will be modeled using the unstructured covariance matrix. The Kenward-Roger approximation will be used to estimate denominator degrees of freedom. Contrasts will be constructed to obtain the treatment effects at each postbaseline visit (i.e., Day 30, Day 90, and Day 180) to compare each AGN-151607 treatment group versus the placebo group. Each treatment effect and treatment comparisons will be estimated by the LS Means and their differences in LS Means, along with their SE and 95% confidence intervals, and the p-value corresponding to the between-treatment group difference.

10.4.2.1 University of Toronto Atrial Fibrillation Severity Scale (AFSS)

A self-reported, disease-specific quality of life instrument used to capture subjective and objective ratings of disease burden in patients with AF. The AFSS consists of 19 items. It contains a visual analogue scale, 4 items on AF frequency, duration and severity that are used to calculate AF burden, 4 items on health care utilization, and 7 items regarding the severity of specific symptoms. See Appendix 10.9 of study protocol for more details.

The tables below show the scoring algorithm for some of the items on the questionnaire as well as the derivation of the following aggregate measures:

- Total AF Burden
- AF Symptoms Score

Question Number (range)	Scoring
Q4 (1-10) Global well-being	Raw score
Q5 (1-11) AF frequency *lower scores denote more frequent AF	Continuous = 1 More than twice a day = 2 Daily or almost daily = 3 4 - 5 times a week = 4 2 - 3 times a week = 5 About once a week = 6 About twice a month = 7 About once a month = 8 About 2-4 times a year = 9 About once a year = 10 Less than once a year = 11
Q6 (1-8) AF duration *lower scores denote AF of longer duration	Continuous = 1 Several days = 2 All day = 3 Several hours = 4 About 1 hour = 5 30 - 45 minutes = 6 < 30 minutes = 7 A few minutes = 8
Q7, Q8 (1-10) AF severity *higher scores denote more severe AF	Arithmetic mean of 2 scores
Q10 (0-7) ER visits	0 = 0 1 = 1 2 = 2 3 = 3 4 = 4 $5 \text{ to } \le 10 = 5$ $> 10 \text{ to } \le 15 = 6$ > 15 = 7
Q11 (0-7) Hospitalizations	0 = 0 1 = 1 2 = 2 3 = 3 4 = 4 $5 \text{ to } \le 10 = 5$ $> 10 \text{ to } \le 15 = 6$ > 15 = 7

 Table 10–1
 The University of Toronto Atrial Fibrillation Severity Scale Scoring Algorithm

Question Number (range)	Scoring
Q12 (0-7) Specialist visits	0 = 0
	1 = 1
	2 = 2
	3 = 3
	4 = 4
	$5 \text{ to} \le 10 = 5$

 $> 10 \text{ to} \le 15 = 6$ > 15 = 7

Table 10-2 The University of Toronto Atrial Fibrillation Severity Scale Scoring Clarifications

CLARIFICATIONS FOR PART A

Total AF Burden

The Total AF Burden has been historically obtained by combining measures of *frequency* (Q5), *duration* (Q6) and patient perceived *severity* (the mean of Q7 & Q8) equally to obtain a score that ranges from 3-30. Though Total AF Burden may be reported as an aggregate measure, we recommend reporting frequency, duration and severity separately as current literature has suggested both frequency and duration are different from severity in that frequency and duration are not well correlated to quality of life however quality of life is driven by patient perceived severity.

Clarifications for Q5 (AF frequency)	Due to the fact that Q5 has responses ranging from 1-11, for patients who respond "Less than once a year", please give them a score of 10 instead of 11 (the response, "About once a year" is also scored as 10). Patients who respond, "Not applicable, I have never had an irregular heart rhythm" will not contribute a frequency score. Suggest reporting the % of N/A
	responses separately with the assumption that these patients may not be aware of their AF frequency. Reverse code scores so that 1=continuously now becomes 10, etc.
Clarifications for Q6 (AF duration)	Take the score of each patient, divide it by 8 and multiply it by 10 so that the score will fall in the range of 1-10. Round to the nearest whole number.
	Patients who respond, "Not applicable, I have never had an irregular heart rhythm" separately will not contribute a duration score. Suggest reporting the % of N/A responses separately with the assumption that these patients may not be aware of their AF duration.
	Reverse code scores so that 1=continuously now becomes 10, etc.
Clarifications for Q7 & Q8 (AF severity)	Add Q7 and Q8 and divide by 2 to obtain the mean. Round to the nearest whole number.

Clarifications to obtain Total AF Burden (AF frequency + AF duration + AF severity)	Total AF Burden=AF frequency + AF duration + AF severity.
	Each of the 3 measures contributes equally to the Total AF Burden score, and each measure varies from 1-10 to yield Total AF Burden scores ranging from 3-30 where higher scores indicate greater AF burden.
CLARIFICATIONS FOR PART B	
Health Care Utilization	
No clarifications for this section.	
CLARIFICATIONS FOR PART C	
AF Symptoms Score	
How affected patients are by specific symptoms related t intolerance, fatigue, etc.	to AF such as palpitations, shortness of breath, exercise
Clarifications to obtain AF Symptoms Score	The AF Symptoms Score is scored in a strictly additive manner. For each of the 7 questions (answers vary from 0=I have not had this symptom in the past 4 weeks to 5=A great deal), the values are determined and summed together to form a total score (from 0-35). This score assumes linearity of severity (i.e., if patient X has a total score of 7 and patient Y has a total score of 35, patient Y has 5x greater severity in symptoms than patient X)
	Note: although the stem question says "How often", in practice this is similar to "How severe were the symptoms when they occurred".

10.4.2.2 Atrial Fibrillation Effect on Quality-of-life (AFEQT) Questionnaire

A questionnaire to assess Health Related Quality of Life (HRQoL) in patients with atrial fibrillation (AF). AFEQT evaluates QoL across 3 domains: symptoms, daily activities and treatment concerns. The questionnaire uses 20 questions on a 7-point Likert scale to measure the overall AFEQT score and treatment satisfaction.

The responses on the AFEQT are scored on a 1 to 7 Likert scale, where for questions 1-18, 1= "Not at all..." to 7 = "Extremely...". Questions 19- 20 relate to patients' satisfaction with treatment and are not included in HRQoL score of the AFEQT questionnaire.

Calculation of the overall AFEQT score is based on the following formula: Overall AFEQT score = 100 - [((sum of severity for all questions answered - number of questions answered) X 100) / (total number questions answered X 6)].

Note that questions 19 and 20 are not included in the derivation of the overall AFEQT score.

Subscale scores are computed similarly to the overall score from each subscale used to generate its own score. The 18 questions are grouped into 3 functional subscales as described below:

Subscales	Questions
Symptoms	1, 2, 3, and 4
Daily Activities	5, 6, 7, 8, 9, 10, 11, and 12
Treatment Concern	13, 14, 15, 16, 17, and 18

The 2 treatment satisfaction questions (Questions 19 and 20) are not part of the overall AFEQT score but are computed as its own subscale similarly to the overall score.

Subscale	Questions
Treatment Satisfaction	19, 20

Overall or subscale scores range from 0 to 100. A score of 0 corresponds to complete disability, while a score of 100 corresponds to no disability.

Separate analyses will be performed for each of the following scores:

- Overall AFEQT score
- Symptoms subscale score
- Daily activities subscale score
- Treatment concern subscale score
- Treatment satisfaction subscale score

10.4.2.3 Duke Activity Status Index (DASI)

A 12-item, self-administered questionnaire which provides a standardized assessment of functional status that uses the patient's ability to perform a set of common activities of daily living to gauge functional capacity. Scoring of the Activity Status Index is shown on the table below.

Questions	Scores (only for response "Yes, with no difficulty") ^a
1	2.75
2	1.75
3	2.75
4	5.50
5	8.00
6	2.70
7	3.50
8	8.00
9	4.50
10	5.25
11	6.00
12	7.50

Table 10–3Duke Activity Status Index (DASI) Score

a All other responses gets a score of zero for that question.

The DASI score is obtained by summing all the scores from the 12 items on the questionnaire. The higher the score (maximum 58.2), the higher the functional status.

10.4.2.4 European Quality of Life - 5-Dimensional - 5-Level (EQ-5D-5L)

The EQ-5D-5L is made up of two components: health state description and evaluation. The description component consists of five dimensions: mobility, self-care, usual activities, pain/discomfort, and anxiety/depression. The mobility dimension queries the participant's walking ability. The self-care dimension queries the participant's ability to wash or dress by himself. The usual activities dimension assesses the participant's performance in "work, study, housework, family or leisure activities". The pain/discomfort dimension measures how much pain or discomfort a participant has. The anxiety/depression dimension assesses how anxious or depressed a participant is. The respondents rate their level of severity for each dimension using a 5-level scale (EQ-5D-5L) by ticking (or placing a cross) in the box against the most appropriate statement in each of the 5 dimensions. The second component of the EQ-5D-5L is a visual analogue scale (EQ-VAS) by which participants can rate their overall health from 0 (worst imaginable health state) to 100 (best imaginable health state).

With the EQ-5D-5L, rating levels can be coded as numbers 1, 2, 3, 4 or 5 which correspond to "have no problems", "have slight problems", "have moderate problems", "have severe problems", and "unable to do/have extreme problems", respectively. As a result, a participant's health state can be defined by a 5-digit number by combining the numeric levels from the 5 dimensions, ranging from 11111 ("have no problems" in all 5 dimensions) to 55555 ("unable to

do/have extreme problems" in all 5 dimensions). The US-based value set for the EQ-5D-5L will be derived using an international standardized protocol (Pickard *et. al.*, 2019).

The EQ-5D-5L will be completed by the participants at Screening, Day 30, Day 90, Day 180 or at early discontinuation visit if necessary.

10.4.2.5 Short Form-12 Health Survey (SF-12v2)

The SF-12v2 health survey is a generic assessment of health-related quality of life from patient's perspective. It consists of 12 items that measures 8 health domain scales: physical functioning (PF), role limitations due to physical health problems (RP), bodily pain (BP), general health (GH), vitality (energy/fatigue) (VT), social functioning (SF), role limitations due to emotional problems (RE), and mental health (physiologic distress and physiologic well-being) (MH). The 8 scales are aggregated into 2 summary measures: the Physical Component Summary (PCS) and the Mental Component Summary (MCS) scores, which range from 0 to 100, with higher scores indicating better quality of life.

Within each scale, if there are less than or equal to 50% of the item scores missing, the missing item score(s) will be imputed using the mean score of the non-missing items and used to calculate the scale score. If more than 50% of the item scores are missing, no imputation will be performed, and the scale score will be set to missing.

The component summary scores will be derived using the following scoring algorithm.

Step 1: Item coding

Code the response to each item as follows such that higher score indicates better health state.

Response Choices	Precoded Item Value	Final Item Value
Excellent	1	5.0
Very Good	2	4.4
Good	3	3.4
Fair	4	2.0
Poor	5	1.0

Response to Item 1

Response to Items 2a and 2b

Respond Choices	Precoded Item Value	Final Item Value
Yes, limited a lot	1	1
Yes, limited a little	2	2
No, not limited at all	3	3

Response to Items 3a, 3b, 4a, 4b and 7

Response Choices	Precoded Item Value	Final Item Value
All of the time	1	1
Most of the time	2	2
Some of the time	3	3
A little of the time	4	4
None of the time	5	5

Response to Item 5

Response Choices	Precoded Item Value	Final Item Value
Not at all	1	5
A little bit	2	4
Moderately	3	3
Quite a bit	4	2
Extremely	5	1

Response to Items 6a, 6b and 6c

Response Choices	Precoded Item Value	Final Item Value
All of the time	1	5
Most of the time	2	4
Some of the time	3	3
A little of the time	4	2
None of the time	5	1

Step 2: Computing raw scale scores

After item recoding, a raw score is computed for each scale which is the simple algebraic sum of the final item values for all items in that scale as shown in the below table. For example, the raw score for PF scale is the sum of the final item values of items 2a and 2b.

Scale	Sum Final Item Values	Lowest and Highest Possible Raw Scores	Possible Raw Score Range
PF	Items 2a + 2b	2, 6	4
RP	Items 3a + 3b	2, 10	8
BP	Item 5	1, 5	4
GH	Item 1	1, 5	4
VT	Item 6b	1, 5	4
SF	Item 7	1, 5	4
RE	Items 4a + 4b	2, 10	8
MH	Items 6a + 6c	2,10	8

Step 3: Transforming raw scale scores

Transforming the raw scale score to a 0-100 scale using the formula below. The table above include the lowest possible and possible range of raw score for each scale.

Transformed scale =
$$rac{Actual raw score - Lowest possible raw score}{Possible raw score range} imes 100$$

For example, the transformed score for PF scale is (Raw PF score - 2) / 4.

Step 4: Standardizing transformed scale scores

Each transformed scale is standardized to a z-score using scale means and standard deviations from the 1998 general United States population as shown in the below table.

Scale	Mean	Standard Deviation
PF	81.18122	29.10558
RP	80.52856	27.13526
BP	81.74015	24.53019
GH	72.19795	23.19041
VT	55.59090	24.84380
SF	83.73973	24.75775
RE	86.41051	22.35543
MH	70.18217	20.50597

The formula for z-score transformation is:

Z-score standardized scale = (Transformed scale score – Mean) / Standard Deviation For example, the z-score of PF scale = (Transform PF score – 81.18122) / 29.10558.

Step 5: Aggregating scale scores to compute raw component summary scores

The standardized scales are aggregated using weights (factor score coefficients) from the 1998 general United States population to derive raw component summary scores (PCS and MCS). Formulae for aggregating z-score standardized scales are:

$$Raw PCS = PF \times .42402 + RP \times .35119 + BP \times .31754 + GH \times .24954 + VT \times .02877 + SF \times -.00753 + RE \times -.19206 + MH \times .22069$$
$$Raw MCS = PF \times .22999 + RP \times -.12329 + BP \times -.09731 + GH \times -.01571 + VT \times .23534 + SF \times .26876 + RE \times .43407 + MH \times .48581$$

Step 6: Standardizing composite summary scores

The raw PCS and MCS scores are standardized as follows such that the final PCS and MCS scores have values with mean 50 and standard deviation 10.

 $PCS = 50 + Raw PCS \times 10$ $MCS = 50 + Raw MCS \times 10$

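### SF-12v2 mental health scale: one shared coding table keys one of its two items the wrong way, so the best and worst mental states get the same score

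*SAP*

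**What the plan says.** **SF-12v2 (SAP 10.4.2.5).** Step 1 sets the aim: "Code the response to each item as follows such that higher score indicates better health state". The scale list describes one domain as "mental health (physiologic distress and physiologic well-being) (MH". The table headed "Response to Items 6a, 6b and 6c" then applies a single map to all three items: *All of the time* = 5, down to *None of the time* = 1. Step 2 forms MH as 6a + 6c, with lowest 2, highest 10 and range 8. Step 3 rescales to 0–100 with an explicit factor of 100, but its example reads "the transformed score for PF scale is (Raw PF score - 2) / 4". Steps 4 to 6 standardise, weight and rescale so that the "final PCS and MCS scores have values with mean 50 and standard deviation 10".

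**AFSS (SAP 10.4.2.1, Table 10-2).** Total AF Burden is the sum of frequency, duration and severity. A participant who answers that they never had an irregular heart rhythm "will not contribute a frequency score" and "will not contribute a duration score". The table suggests reporting the share of such answers and recommends reporting the three components separately. It does not say what the total is when two components are absent.

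**Analysis (SAP 10.4.2).** "The change from baseline in each of the aggregate scores will be analyzed using a mixed model for repeated measures (MMRM", with the baseline score as a covariate.

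**The concern.** If MH has only two items and covers both distress and well-being, one item carries each. A single map cannot then make a higher value better for both. The printed sum would add a correctly keyed item to a reversed one, and the two would cancel for anyone who answers consistently. MH feeds both MCS and PCS, and the SAP plans MMRM contrasts with confidence intervals and p-values on aggregate quality-of-life scores. The error favours neither arm by design. It removes the mental health signal from MH and distorts both summary scores.

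The AFSS question is different in kind. In a prevention trial, whether a participant has a frequency and a duration score may depend on having had AF. The plan should therefore say how such participants enter a change-from-baseline model.

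**Working it through.** **Inputs, all from SAP 10.4.2.5:** the coding table for 6a, 6b and 6c; MH = 6a + 6c; MH norm mean 70.18217 and SD 20.50597; MH weights 0.48581 (MCS) and 0.22069 (PCS); final scaling of 10 points per raw unit.

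**1. The plan's own range reproduces.** Lowest raw MH is 1 + 1 = 2, highest is 5 + 5 = 10, range 8, as printed. The fault is in direction, so a range check would not find it.

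**2. Score consistent respondents both ways.** Transformed MH = (raw − 2) / 8 × 100. The redirected coding gives the distress item *All of the time* = 1 up to *None of the time* = 5.

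| State | Well-being answer | Distress answer | Printed raw → MH | Redirected raw → MH |
|---|---|---|---|---|
| Best | All | None | 5 + 1 = 6 → 50 | 5 + 5 = 10 → 100 |
| Good | Most | A little | 4 + 2 = 6 → 50 | 4 + 4 = 8 → 75 |
| Middle | Some | Some | 3 + 3 = 6 → 50 | 3 + 3 = 6 → 50 |
| Poor | A little | Most | 2 + 4 = 6 → 50 | 2 + 2 = 4 → 25 |
| Worst | None | All | 1 + 5 = 6 → 50 | 1 + 1 = 2 → 0 |

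All five get 50 as printed. A respondent who answers *All of the time* to both items gets (10 − 2) / 8 × 100 = 100, where the redirected coding gives 50. Over all 25 answer pairs, weighted equally, the printed and redirected scores have correlation 0: one depends on the sum of the two printed item values and the other on their difference.

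**3. Carry the error into the summary scores.**

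- MH z-scores: printed (50 − 70.18217) / 20.50597 = −0.984; redirected best (100 − 70.18217) / 20.50597 = +1.454; redirected worst (0 − 70.18217) / 20.50597 = −3.423.
- At either extreme MH is off by 50. MCS: 10 × 0.48581 × 50 / 20.50597 = 11.85. PCS: 10 × 0.22069 × 50 / 20.50597 = 5.38.
- At good or poor MH is off by 25. MCS: 5.92. PCS: 2.69.
- At the middle the error is 0.

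**4. Missing items.** The SAP fills a missing item with the mean of the answered ones when no more than half are missing. For MH this copies the single answered item. Under the printed table the result is right if the well-being item was answered and fully inverted if the distress item was. For example, a best-state respondent with only the distress item answered gets 1 + 1 = 2, MH 0 instead of 100.

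**5. Worked physical functioning (PF) example.** For the best answers (raw 6) the Step 3 formula gives (6 − 2) / 4 × 100 = 100, and the example gives 1. Using the PF mean 81.18122 and SD 29.10558, z is (100 − 81.18122) / 29.10558 = +0.65 against (1 − 81.18122) / 29.10558 = −2.75. The formula governs, so this is an editorial slip.

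**6. AFSS.** Three components of 1–10 each give 3–30, as printed, and no wrong value arises. The gap is the step from two absent components to a total, and from that total to a change from baseline. Prior paroxysmal AF is allowed at entry but not required (Protocol 5.1, criterion 6.01), so some participants can be expected to give this answer at baseline. The documents do not give the share with prior AF, so I put no number on the loss.

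**The case against.** **The item wording is not shown.** This stands in part: the documents do not identify which of 6a and 6c is the distress item. The contradiction does not depend on knowing, and its size is the same either way.

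**The largest error applies only at the extremes.** This stands. The error halves at intermediate states and vanishes at the middle. A reader might infer that MCS and PCS lose their meaning. The documents do not support that, because the other seven scales are untouched by this coding fault.

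**A programmer would use the licensed manual anyway.** Possibly, but the SAP states that the component scores will be derived by the printed steps.

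**The PF example could be read as a second scoring error.** It is not one. The stated 0–100 scale and the printed factor of 100 both override it.

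**A reader might question the signs of the printed weights** (for example, MH positive in PCS beside a negative role-emotional weight). These cannot be settled without the manual, and a sign may have been lost in text extraction. The size of the PCS error uses the printed weight, and its direction depends on that sign.

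**A reader might infer that AFSS scoring gives wrong results, or that burden is missing for everyone who never had AF.** Neither follows. The trigger is a self-reported answer, and Table 10-2 assumes that these participants may simply be unaware of their AF. The SAP does not say that the total is missing. It already suggests tabulating these answers, and the AF Symptoms Score keeps such participants through its zero category. Scoring them 0 would conflict with that assumption and fall outside the 3–30 scale. What remains is an unstated missing-data rule.

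**Conclusion.** The SF-12v2 fault is real and follows from the SAP's own text. The shared table cannot satisfy the Step 1 rule for both MH items, and consistent respondents from best to worst all score 50. The error is up to 11.8 points in MCS and 5.4 in PCS on scales with SD 10. This assumes that one MH item measures distress and the other well-being, as the scale description implies, and that the printed weights and norms apply.

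The PF example is editorial. The AFSS matter is a missing-data rule to be stated. All of these are exploratory quality-of-life outcomes (SAP 5.5 and 10.4), and the primary and secondary endpoints are unaffected.

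**What to change.** 1. Identify the distress item from the questionnaire and give it its own table: *All of the time* = 1 up to *None of the time* = 5. The SAP already prints this map for items 3a, 3b, 4a, 4b and 7. Keep the current table for the well-being item and 6b.
2. Check the item keys and the printed weights against the licensed scoring manual before programming. Test the code on one best-state and one worst-state record, which should give MH 100 and 0.
3. Add × 100 to the worked PF example.
4. State how Total AF Burden is handled in the change-from-baseline MMRM for participants who answer that they never had an irregular rhythm, at baseline and after. The rule should respect the SAP's assumption that they may be unaware of their AF. Keep the separate reporting of components and of the share giving this answer.

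The cost is one coding table, one corrected example, one sentence on AFSS and the matching scoring code. No new data or participants are needed. If SF-12v2 scores have already been produced from the printed table, they need to be re-run.
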